The investigators have designed the study to include two weeks (from Week 12 to Week 14) to monitor the patient for drug discontinuation or withdrawal symptoms. The investigators will treat emergent psychological symptoms with psychosocial support and physical symptoms with the appropriate treatments, such as metoclopramide for nausea, NSAIDs for pain, clonidine for opioid-like withdrawal symptoms, and loperamide for diarrhea. Three to five days after Week 12 discontinuation of medication, the research nurse will call participant to check on emergent adverse symptoms

A caution that is included in the informed consent stating that in a situation when analgesia may be required in a patient who has received full blocking doses of XR-NTX, consideration should be given to regional analgesia, conscious sedation with a benzodiazepine, use of non-opioid analgesics, or general anesthesia. If opioid analgesia is required, the amount of opioid needed may be greater than usual, and the resulting respiratory depression may be deeper and more prolonged. In this case, a rapidly acting opioid analgesic that minimizes the duration of respiratory depression is preferred. XR-NTX can also diminish the benefit from opioid-containing cough, cold, and antidiarrheal preparations, which is listed as a warning in the informed consent. These warning are standard when treating patients with XR-NTX.

Side effects of XR-NTX that led to more discontinuation of treatment compared to placebo include the following: pain, tenderness, induration or pruritus at the site of the injection (3%), nausea (2%), headache (1%), and suicide-related events (0.3%). Other known non-serious side effects that differ from placebo include nausea (29% vs 11%), vomiting (12% vs 6%), diarrhea (13% vs 10%), abdominal pain (11% vs 8%), injection site reactions (65% vs 50%), arthralgia/arthritis (9% vs 5%), muscle cramps (5% vs 1%), rash (6% vs 4%), headache (21% vs

18%) dizziness (13% vs 4%), somnolence/sedation (5% vs 1%), and appetite decrease (11% vs 3%). XR-NTX has the capacity to cause hepatocellular injury when given in excessive doses (the margin of separation between the apparently safe dose of naltrexone and the dose causing hepatic injury appears to be five-fold. XR-NTX does not appear to be a hepatotoxin at the recommended doses used in this study.

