5.4 PARTICIPANT WITHDRAWAL OR TERMINATION

5.4.1 REASONS FOR WITHDRAWAL OR TERMINATION

Participants may discontinue study treatment or withdraw from participation in the study at any time without cause or reason. Participants may stop study medication but are encouraged to

remain in the study for follow-up assessments. The investigator may discontinue study treatment for a participant or withdraw a participant from the study for one or more of the following reasons:

- The participant's expressed desire to end his/her participation in the study.
 - Note: The participant may choose to stop the study drug but continue in the study for data collection and is thus not withdrawn from the study.
- A clinically significant adverse event (AE), laboratory abnormality, or other medical condition or situation that makes continued participation in the study to be not in the best interest of the participant
- The participant demonstrates an inability to comply with the verbal and written study instructions and/or procedures, (i.e., loses the capacity to provide informed consent)
- The participant exhibits unsafe behaviors (e.g., abusive, aggressive) or becomes suicidal, homicidal, or psychotic, (i.e., at significant risk of harming self or others).
- The participant has an intolerable adverse reaction to a study medication.
- The participant's underlying condition is worsening and needs alternative treatment(s)
- The study is canceled by the PASA Consortium, DoD, or investigators.
- The study is closed by the Data Safety and Monitoring Board (DSMB), Institutional Review Board (IRB), or other oversight committee.
- New information regarding the safety of a study medication emerges that changes the risk benefit profile for a sub-group of participants

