5.4.2 HANDLING OF PARTICIPANT WITHDRAWALS OR TERMINATION

If an early exit occurs, the reason(s) for early termination is documented and all Week 12 procedures are conducted. A post-study phone call or visit is scheduled with the research team to ensure that the participant has made or scheduled the appropriate follow-up appointments and to address any clinical problems or AEs that may have occurred.

Participants may stop study medication but are encouraged to remain in the study for follow-up assessments. In this case, the participant may attend assessments for data collection or consent to allow for continued follow-up through chart review. If a participant withdraws from the interventional portion of a study and does not consent to continued follow-up of associated clinical outcome information, then the investigators will not access the participant's medical record or make future contact with the participant. If a study participant withdraws consent for study participation, then the participant is excluded from all future study procedures and treatments. No additional study data is collected from the participant after consent has been withdrawn.

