7.3.4 FOLLOW-UP VISITS

Assessments occur at screening, baseline, and post-randomization Weeks 1, 2, 4, 6, 8, 10, and 12. There is a visit window of +/- 7 days for follow-up visits.

The investigators and CRCs provide ongoing reinforcement of the patients' commitment to long-term follow-up. The study medication providers emphasize the need to properly adhere to prescribed treatments or to call to revise the treatments if side effects occur or therapeutic effects are lost.

Adherence to SL-BUP medication is confirmed by pill count. Concomitant medications are updated at each of these visits.

If participants experience side effects that cannot be managed by adjustments in the timing of the medication (i.e., taking at bedtime, etc.), they may have their medication titration either held or the medication dosing may be decreased (i.e., less frequent).

The CRC makes a telephone (t) contact with the participant between face-to-face visits to remind the participant of the next office visit and to check on adherence to the study medication and if there have been any serious adverse events.

*Psychophysiological assessments are optional to not be a barrier to enrollment or randomization.

The one-day psychophysiological assessment is repeated at Week 2.

The two-day psychophysiological assessment is repeated at Week 8.

At Week 8, the participant remains on the assigned treatment and dose from Week 8 to Week 12.

While every attempt is made to retain the participant in the study on medication for the full 12 weeks, the participant may discontinue medication at any point and remain in the study for assessments through Week 12.

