10.4.4 SAFETY ANALYSES

The safety analyses population includes all randomized participants. These analyses will include those participants who have reported an adverse event as well as those who do not report an adverse event. The incidence of treatment emergent adverse events, type of adverse events, and frequency of withdrawals due to an adverse event will be summarized by treatment group. Appropriate statistical comparisons will be made between treatment groups in terms of 1) rates of adverse events, 2) discontinuation due to adverse events, and 3) side effect scales. Rates will be compared using time to event hazard analysis. Frequencies will be analyzed using the chi square or Fisher Exact test. The scales will be examined using non-parametric analyses when appropriate. This study is not powered as an equivalence study so the non-significance of differences between groups does not truly imply equivalence.

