7.9 Assessment Windows

All screening assessments will be performed prior to Day 0 (study baseline/admission). Screening will take place over 1 to 14 days and include the study instruments listed in the table above (section 4.5). Most screening assessments are repeated at Day 0 if occurring more than one-month post screening. The most recent data collected during the screening/baseline period will be used for summarizing and analyzing baseline data.

Participants will visit their respective site to complete study procedures at weeks 1, 2, 4, 6, 8, 10, and 12. The visit windows for these in-person visits is +/- 7-days. It is important to confirm

appointment with subjects at each visit, so that if adjustments need to be made so that the subject does not run out of medication between the scheduled in-person visits. The CRC will make a telephone contact with the participant between face-to-face visits to remind the participant of the next office visit and to check on adherence to the study medication and if there have been any adverse events. While every attempt is made to retain the participant in the study on medication for the full 12 weeks, the participant may discontinue medication at any point and remain in the study for assessments through week 12. Out-of-window visits or assessments must be reported as protocol deviations. If any exclusions are made for these reasons, these exclusions will be described in the study report.

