Phosphatidyl ethanol (PEth)	Continuous (range between 0 and >210 ng/mL)	
Phosphatidyl ethanol (PEth) are a series of abnormal phospholipids located in the cell membrane and formed in the presence of ethanol and phospholipase D. PEth serves as a biomarker of alcohol ingestion in the past 2-3 weeks using liquid chromatography tandem mass spectrometric assessment of human blood (whole or dried spots). PEth in blood is often used as a marker of chronic alcohol use and was collected at baseline and weeks 8 and 12.
 
At the present time, the international scientific community has not yet established a cut-off value for PEth concentration in blood to be used for differentiating an acceptable social ethanol intake (<40 g for males and <20 g for females, according to the WHO parameters), from an at-risk-alcohol-use (40–60 g/die) and chronic excessive drinking behavior (>60 g/die). However, per LabCorp, PEth levels in excess of 20 ng/mL are considered evidence of moderate to heavy ethanol consumption.

Safety Outcomes		
Adverse Events	Counts and proportions	Total number and proportion of treatment emergent adverse events. Comparison of AE rates by treatment group will also be stratified by type and severity.
Withdrawals due to Adverse Events	Proportion	Proportions of individuals by treatment group who withdrew from the study due to adverse events
Adherence and Retention Outcomes		

Variable	Type	Definition
Serum Buprenorphine and Norbuprenorphine	Continuous	
Buprenorphine and its metabolite norbuprenorphine are assayed using liquid chromatography tandem mass spectrometry by a commercial laboratory. Sample results are available via the commercial laboratory portal using a study specific username/password combination and the unique participant code/requisition number.
 
To assess medication adherence, blood samples collected at study weeks 8 and 12 will be tested for buprenorphine and its metabolite, norbuprenorphine, using quantitative assessments.

Pill Count	Count and proportion	
A dosing log case report form (CRF) is completed weekly (or since the last in-person visit) for each participant. The number of completed NTX injections received (at baseline, week 4, and week 8) is recorded, as well as the number of missed SL-BUP pills per week. For each medication (NTX and SL-BUP), the proportion of subjects who missed any treatment will be derived, as well as the total number of missed injections or pills, per participant.

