9.5 Safety Analysis Methods

9.5.1 Adverse Events

Any AEs will be listed and summarized by system organ class and preferred event term. Summaries will include the number of individuals experiencing events over the duration of the study. These summaries will be created for all AEs and AEs by severity (mild or moderate vs. severe or greater). Summaries will be provided by treatment group. If models can be run, point and confidence interval estimates of the risk difference will be obtained by modeling the probability of experiencing at least one adverse event. The model is specified with the equation:

$$g(E(Y_{ij})) = \beta_0 + \beta_1 \text{Treatment}_{ij} + s_i + \varepsilon_{ij}$$

Where $g(E(\cdot))$ indicates the identity link function on the expected value of Y , Y_{ij} is the occurrence of an AE outcome (any AE, any SAE, and any related AE) in subject i , β_0 is the intercept, β_1 is the treatment group coefficients, s_i is a random subject effect, and ε_{ij} is the residual error term.

Point and confidence intervals for the difference in experienced AE proportion between treatment groups will be estimated with a generalized linear mixed model (GLMM), assuming a binomial distribution and identity link. GLMMs are a flexible generalization of the linear mixed effect model that allows response outcomes to have an error distribution other than the normal distribution (McCullagh, & Nelder, 1989). Statistical analysis modeling will be carried out utilizing SAS/STAT PROC GLIMMIX (SAS Institute Inc. 2017) with the general structure of the SAS code for this model is listed below:

```
proc glimmix data=anlyaedata;
  class patient treatment;
  model any_ae = treatment / link=identity dist=binomial;
  random int / subject=patient;
run;
```

A similar model will be run for the difference in proportion of withdrawn subjects due to adverse events between treatment groups. If the above specified models cannot be fit due to limitations of the study data, frequencies will be analyzed using chi-square test.

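### The SAP counts only study withdrawals due to adverse events, so a participant who stops study drug for an adverse event but stays for follow-up is a non-event, and no other SAP item reports such stops by arm

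*SAP*

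**What the plan says.** The SAP outcome table (9.2) has a row for withdrawals due to adverse events, defined as "Proportions of individuals by treatment group who withdrew from the study due to adverse events". SAP 9.5.1 gives its analysis: "A similar model will be run for the difference in proportion of withdrawn subjects due to adverse events between treatment groups", with a chi-square test if the model cannot be fitted.

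The protocol treats stopping drug and leaving the study as separate events. A note in Protocol 5.4.1 says the participant may choose to "stop the study drug but continue in the study for data collection and is thus not withdrawn from the study". Protocol 5.4.2 adds: "Participants may stop study medication but are encouraged to remain in the study for follow-up assessments". Protocol 7.3.4 says that "the participant may discontinue medication at any point and remain in the study for assessments through Week 12", and SAP 7.9 repeats this.

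Protocol 10.4.4 plans two things: a summary by treatment group of how often participants withdraw due to an adverse event, and between-group comparisons whose second item is "2) discontinuation due to adverse events". It does not say whether discontinuation means of drug or of study.

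**The concern.** The event in the SAP is leaving the study. The event most directly tied to how well the regimen is accepted is stopping the drug. The protocol separates the two and steers stoppers towards staying in follow-up. That is good for the efficacy data, but it makes the SAP outcome depend on retention: the more adverse-event stoppers are kept in follow-up, the fewer events it records. A low figure could then reflect good follow-up rather than few treatment-ending adverse events.

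The two arms need not be affected equally. Protocol 2.3.1 introduces its list of reasons for stopping with "Side effects of XR-NTX that led to more discontinuation of treatment compared to placebo". If that pattern recurs here, more of the uncounted stops would fall on the active arm, and the between-arm contrast would shrink.

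**Working it through.** The documents give no expected rate, power or sample size for this outcome, so there is no planned figure to reproduce. The check is a reading of the definitions, then an illustration.

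**Step 1. Classify one participant.** Take someone who stops the tablets or injection because of an adverse event and attends visits through Week 12.
- Protocol 5.4.1: not withdrawn from the study.
- SAP 9.2 and 9.5.1: the event requires withdrawal from the study, so this person is a non-event.

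**Step 2. Look for another SAP item that captures the stop, with its cause, by arm.**
- SAP 8.1: a summary of those completing or discontinuing study therapy; no adverse-event cause and no arm comparison is stated.
- SAP 8.3: a listing of missed doses with reasons; descriptive, not an outcome.
- SAP 9.2 (pill count) and 9.6.2: missed pills and injections, by treatment group in 9.6.2; no cause.
- SAP 9.5.1: incidence of any adverse event, any serious event and any related event; shows that an event occurred, not that it ended treatment.
- SAP Appendix B: no table of treatment discontinuation.

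None gives adverse-event-attributed drug discontinuation by arm.

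**Step 3. Size.** Let q be the share of an arm stopping drug for an adverse event and s the share of those stoppers who stay in the study. With 45 per arm (Protocol 10.5):

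- actual drug stops = 45 × q
- events recorded by the SAP = 45 × q × (1 − s)
- proportion missed = s

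The documents do not give s, so it runs from 0 to 1. For q, Protocol 2.3.1 lists 3%, 2%, 1% and 0.3% for XR-NTX. Assuming no overlap, 3 + 2 + 1 + 0.3 = 6.3%, and 45 × 0.063 = 2.8. Values of 3% and 10% are added as assumed alternatives.

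| q | Actual stops of 45 | Recorded, s = 0.25 | s = 0.5 | s = 0.75 | s = 1 |
|---|---|---|---|---|---|
| 3% | 1.4 | 1.0 | 0.7 | 0.3 | 0 |
| 6.3% | 2.8 | 2.1 | 1.4 | 0.7 | 0 |
| 10% | 4.5 | 3.4 | 2.3 | 1.1 | 0 |

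At s = 0 the SAP outcome records every stop.

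**Step 4. Can the definition change a comparison?** Two-sided Fisher exact tests on hypothetical counts:
- 6/45 vs 0/45 drug stops, p = 0.026; if three of the six stay, 3/45 vs 0/45, p = 0.24.
- 8/45 vs 1/45, p = 0.030; if four of the eight active-arm stoppers stay, 4/45 vs 1/45, p = 0.36.

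Both starting counts exceed the 2.8 from Step 3. At about that rate, 3/45 vs 0/45 already gives p = 0.24, so the comparison would be non-significant under either definition. What changes there is the reported count.

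**The case against.** The strongest reply is that the SAP does implement something the protocol planned. Protocol 10.4.4 calls for a summary of withdrawals due to an adverse event, and the SAP row delivers it. A reader might infer that the SAP replaced the discontinuation comparison with a weaker one. The documents do not show that, because discontinuation in 10.4.4 could mean drug or study. But 10.4.4 lists it apart from withdrawals, and the SAP neither resolves the term nor supplies the drug reading.

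It is also tempting to say that such a participant is counted as having tolerated treatment. The SAP never uses that label. The adverse event still enters incidence by arm, type and severity, and the stop may show in the missed-dose listing. This limits the harm but does not supply the missing outcome.

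A reader might further infer that most of these events will be lost, or that the loss falls almost wholly on active drug. Neither is supported. No document gives the share who stay, and the expected all-cause attrition of about 30% (Protocol 10.5; 0.30 × 45 = 13.5 per arm) means many departures are foreseen. Protocol 2.3.1 gives injection-site reactions of 65% vs 50% on placebo, so some placebo stoppers would be missed too. The direction is plausible; its size is unknown.

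Finally, Protocol 10.4.4 warns that non-significance is not equivalence, and SAP 7.7 treats comparisons other than the primary and secondary tests as descriptive. Both reduce the risk of a false claim of equal acceptability. Neither corrects the count.

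**Conclusion.** The point holds as a definitional gap in a safety outcome. Following the SAP as written, adverse-event drug stoppers who stay in the study are non-events, and their stops are not reported by cause and arm anywhere else. The undercount equals the share of such stoppers who stay, and the supportable range is 0 to 100%. In the illustration, about 2.8 stops among 45 would be recorded as anything from 2.8 down to 0. This assumes that the four XR-NTX rates do not overlap and carry over to this trial, and it makes no allowance for buprenorphine.

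Adverse-event incidence, the sample size and the primary efficacy test are unaffected. The change should be made because the protocol names the comparison and the SAP, as worded, does not deliver it under the drug reading.

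**What to change.** In SAP 9.2 and 9.5.1, add an outcome: permanent discontinuation of the injection and/or the sublingual tablet (active or placebo) due to an adverse event, whether or not the participant remains in the study, compared by arm. Keep study withdrawal due to an adverse event as its own line, and add the matching table to Appendix B.

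Take the reason for stopping from the missed-dose reasons (SAP 8.3) and the adverse-event records. Before unmasking, confirm that this reason is captured for non-serious events. It should not be assumed that the data already exist: Protocol 8.4.2 asks for the action taken with study drug in serious-event reports, whereas the general adverse-event items in Protocol 8.3 do not include it. The early-termination reason (Protocol 5.4.2) covers only those who exit.

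The cost is SAP wording, one extra table row and possibly some coding of reasons. The reported figure may look less favourable. No treatment rule, sample size or alpha changes.

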9.3 Primary Efficacy Analysis Methods

The primary outcome for this study is a binary measure assessed at weeks 4, 8, and 12. A positive response is defined as a decrease from baseline of at least 10 points on the CAPS-5 score (Schnurr et al., 2022) and a reduction of at least 1 risk level of alcohol use, as defined by WHO (Knox et al. 2018). The treatment effect on comorbid PTSD + AUD over time will be assessed using a mixed logistic regression model. The model will be used to generate point and interval estimates of the risk differences and to test differences in proportions of PTSD+AUD resolution between treatment groups at the 8-week visit (primary timepoint), as well as at weeks 4 and 12 (secondary timepoints). The model will include fixed effects for the treatment group, visit (as a categorical variable), gender, site, presence/absence of anti-depressants, treatment-by-visit interaction, and random effects for participant (see model statement below). This approach will provide consistent estimates and valid inferences under missing at random (MAR) data assumptions while accounting for correlation among multiple measures on the same participant. This mixed model will improve the power of the study and the precision of all estimates by allowing all available measures for an individual to be incorporated in the analysis, even if other timepoints are missing. Sensitivity analysis maybe considered by excluding participants that have a low or moderate WHO risk level at baseline. This model is further described below:

$$g(E(Y_{ij})) = \beta_0 + \beta_1 \text{Visit}_{ij} + \beta_2 \text{Site}_{ij} + \beta_3 \text{Treatment}_{ij} + \beta_4 \text{Gender}_{ij} + \beta_5 \text{Anti-depressant}_{ij} + \beta_6 (\text{Treatment} * \text{Visit})_i + s_i + \varepsilon_{ij}$$

Where $g(E(\cdot))$ indicates the identity link function on the expected value of Y , Y_{ij} is the j th measure of PTSD+AUD measurement in subject i , β_0 is the intercept, β_1 through β_6 are coefficients, s_i is a random subject effect and ε_{ij} is the residual error term.

Statistical analysis modeling will be carried out utilizing SAS/STAT PROC GLIMMIX (SAS Institute Inc. 2017) with the general structure of the SAS code for this model is listed below. Generalized linear mixed models (GLMMs) are a flexible generalization of the linear mixed effect model that allows response outcomes to have an error distribution other than the normal distribution (McCullagh, & Nelder, 1989). The GLMM will employ random intercepts for the between participants' part of the covariance model, and the within participants' part of the covariance model will be initially assumed as autoregressive. The study's primary hypothesis will be tested and associated odds ratio obtained using the 'oddsratio' statement which estimates the risk difference in PSTD+AUD resolution between the treatment arms.

```
proc glimmix data=anlydata;
  class patient treat gender visit site antidepress;
  model primoutcome = treat gender visit site antidepress
    treat*visit/ solution link=logit dist=binary oddsratio;
    random int / type=ar(1) subject=patient;
    ods select parameterestimates Oddsratios;
run;
```

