10.4.2 ANALYSIS OF THE PRIMARY EFFICACY ENDPOINT(S)

The primary dependent variable will be response status at Week 8 for each participant. A positive response is defined as a decrease from baseline of at least 8 points on the CAPS-5 score and a reduction of at least 1 risk level of alcohol use, as defined by WHO, at Week 8. Response data will be analyzed using mixed logistic regression with treatment group, measurement visit as a categorical variable, gender, site, presence/absence of anti-depressants, and other potential confounders as explanatory variables. A treatment group by measurement visit interaction will be included to account for the longitudinal nature of the data with the Week 8 effect being the primary outcome of interest. A two-sided p-value will be reported from the primary analysis for the all pairwise comparisons of SL-BUP/XR-NTX treatment and placebo groups.

As a complement to the primary outcome, the AUD and PTSD components of the composite will be evaluated individually. Difference in heavy alcohol use at Week 8 (defined as *>4 standard drinks/sessions for men and >3 standard drinks/sessions for women*) will be analyzed using a generalized-linear mixed model with treatment group, gender, site, presence/absence of anti-depressants, and other potential confounders as explanatory variables. Difference in reduction of PTSD symptoms at Week 8 (as measured by the CAPS-5) will be analyzed using a generalized-linear mixed model with treatment group, gender, site, presence/absence of anti-depressants, and other potential confounders as explanatory variables. For both outcomes, a treatment group by visit interaction term will be included to account for the longitudinal nature of the data, with Week 8 effect being the primary outcome of interest.

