7.7 Multiple Comparisons and Multiplicity

One single primary formal hypothesis test is planned for this study at the 0.05 level of significance, which is the comparison of the SL-BUP + XR-NTX treatment group vs. placebo for the primary outcome at the primary timepoint (Week 8). Additionally, regardless of significance of the primary outcome, statistical significance of the secondary outcomes will be assessed, with adjustment for multiple comparisons using the Benjamini-Hochberg false discovery rate correction to maintain the nominal alpha level of 0.05 (Benjamini & Hochberg, 1995). Primary and secondary hypothesis tests resulting in nonsignificant p-values will be interpreted as inconclusive. All other treatment group comparisons will be considered descriptive in nature with no adjustment for multiple comparisons, and all confidence intervals will be generated using 95% bounds.

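### SAP 9.3 promises a Week 8 risk difference and states an identity link, but its code fits a logit model that outputs odds ratios, so the promised primary estimate is not produced

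*SAP*

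**What the plan says.** Protocol 10.4.2 sets the model and the timepoint: "Response data will be analyzed using mixed logistic regression with treatment group" and other terms, including a treatment-by-visit interaction, "with the Week 8 effect being the primary outcome of interest". SAP 7.7 allows one formal test, active treatment against placebo at Week 8.

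The SAP 9.3 text says that the treatment effect "will be assessed using a mixed logistic regression model". It then says "The model will be used to generate point and interval estimates of the risk differences" and names Week 8 as the primary timepoint, with Weeks 4 and 12 secondary. Below the model equation, g "indicates the identity link function on the expected value of" Y.

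The SAP 9.3 code, offered as a general structure, uses `link=logit dist=binary oddsratio` and an ODS SELECT line that keeps only the parameter estimates and odds ratios. The text describes the odds-ratio option as a "statement which estimates the risk difference in PSTD+AUD resolution between the treatment arms". The same paragraph says that the within-participant covariance starts as autoregressive, and the code puts `type=ar(1)` on a random intercept.

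SAP 7.1 adds that the first models include participants from the discontinued high-dose arm, if the model converges.

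**The concern.** The primary result needs one effect measure, and SAP 9.3 gives two as if they were the same. A programmer who follows the equation and the promise would report a risk difference. One who follows the code would report an odds ratio. A reader who trusts the sentence linking them would take an odds ratio for a difference in proportions and misjudge the size of the effect.

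Two smaller mismatches sit in the same code. Nothing in it isolates the Week 8 comparison of 2 mg with placebo, and the stated autoregressive structure is not what is coded.

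**Working it through.** **1. Text against code in SAP 9.3**

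| Item | Text | Code |
|---|---|---|
| Model | Mixed logistic | Logit link, binary |
| Link in equation | Identity | Logit |
| Effect measure | Risk difference with interval | Coefficients and odds ratios only |
| Timepoint | Week 8 primary | `treat` and `treat*visit`, no Week 8 statement |
| Within-participant covariance | Autoregressive | `type=ar(1)` on one random intercept |

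The text also disagrees with itself (logistic against identity). Elsewhere the SAP codes both missing pieces: the CAPS-5 code in 9.3.1 has `lsmeans treat*visit`, and the adverse-event code in 9.5.1 really does use `link=identity`.

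**2. The plan's own figure.** Inputs from SAP 6 and Protocol 10.5: 45 per arm, 5/45 vs 17/45, two-sided 0.05, Fisher's test with the Walters approximation. With the continuity correction 1/(2 × 45) = 0.0111:

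- d = √90 × [asin√(0.3778 − 0.0111) − asin√(0.1111 + 0.0111)] = 9.487 × (0.6504 − 0.3572) = 2.782
- power = Φ(2.782 − 1.960) = 0.795, as in the protocol table.

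This power rests on Fisher's test and not on the mixed model, so the present point does not change it.

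**3. The two measures at the planning counts**

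- Risk difference = 17/45 − 5/45 = 0.267. SE = √(0.378 × 0.622/45 + 0.111 × 0.889/45) = 0.0861. 95% CI 0.098 to 0.435.
- Marginal odds ratio = (17/28)/(5/40) = 4.86. SE of log = √(1/17 + 1/28 + 1/5 + 1/40) = 0.565. 95% CI 1.60 to 14.7.
- One does not determine the other. An odds ratio of 4.86 gives a risk difference of 0.140, 0.267 or 0.348 at placebo rates of 4% (2/45), 11% (5/45) or 20% (9/45).

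**4. What the random-intercept model reports.** Its odds ratio is conditional on the participant. For an intercept SD σ, solve E[expit(η + σZ)] = 5/45 and 17/45 with Z standard normal, then take exp(η₁ − η₀). The result is 6.24, 11.36 and 23.95 for σ = 1, 2 and 3. The documents give no σ, so these values are assumptions.

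**5. Effect on significance.** This is a single-visit, unadjusted proxy: an unpooled Wald test on the risk difference against a Wald test on the log odds ratio, enumerating all tables at 5/45 vs 17/45.

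| Per arm | Tests disagree | Counting empty-cell tables as non-significant on log-odds |
|---|---|---|
| 45 | 1.6% | 2.1% |
| 36 (20% missing) | 2.5% | 3.9% |
| 32 (about 30% missing) | 6.0% | 8.2% |

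Only borderline data are affected. With 45 per arm, 4 vs 11 responders gives p = 0.043 (risk difference) and 0.056 (log-odds). The pair 5 vs 13 is significant on both scales (0.031, 0.041), and 5 vs 12 on neither (0.054, 0.067).

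**6. The Week 8 contrast.** With the interaction in the model, the `treat` coefficient alone is the effect at the reference visit, and the code sets no reference. The Week 8 log odds ratio is the sum of the `treat` and the Week 8 interaction coefficients. Its variance needs their covariance, which a table of coefficients and standard errors does not give. With the high-dose arm included, `treat` has three levels, so the pair must also be named.

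**7. Covariance.** One intercept per participant makes a 1 × 1 matrix. It has no lag, so AR(1) has nothing to act on.

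**The case against.** The strongest defence is that the intent is clear. Protocol 10.4.2, SAP 7.7 and SAP 9.3 all fix Week 8, the code is only a general structure, and logistic regression is named in both documents. In this logit model, a Week 8 log odds ratio of zero and a standardised Week 8 risk difference of zero are the same null, so a logit test does test a difference in proportions. The identity wording has the same form as in the adverse-event section, where it matches the code, so carry-over is plausible. Finalising the SAP before lock (Protocol 10.1) and unmasking only after lock (SAP 4.4.2) limit any later choice.

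Most of this stands. A reader might infer that the primary visit is open, or that the primary p-value could properly come from Week 12 or an average over visits. The documents do not support that, because the prose excludes both. Nor do they show what the odds-ratio table prints when an interaction is present; that is a matter of software, so it cannot be asserted that the table lacks a Week 8 row. A reader might also infer bias from the autoregressive mismatch, but nothing here shows any.

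The defence does not reach the link definition or the sentence equating the odds ratio with the risk difference. Both are prose, not sketch code, and both are wrong. It also leaves the promised risk difference without a method.

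**Conclusion.** The point holds as an internal contradiction on the primary effect measure, and it should be fixed before unmasking. The promised Week 8 risk difference and its interval are not produced, and the quantity that is produced is mislabelled. The consequence lies mainly in how the effect is reported: 0.267 against a marginal odds ratio of 4.86, or a subject-specific one of 6.2 to 24.0 under the assumed intercept SDs of 1 to 3.

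A reader might infer that the choice of scale could decide the trial. The figures do not support that. Disagreement is about 1.6% at full size and 6% if all of the planned attrition of about 30% is missing at Week 8. These rates rest on the planning response rates and on a single-visit Wald proxy without covariates.

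The missing Week 8 statement is a matter of aligning the code with prose that is already clear. The AR(1) mismatch is minor.

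**What to change.** Before unmasking:

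1. In the model description of SAP 9.3, replace the identity link with the logit link.
2. Delete the clause saying that the odds-ratio option estimates the risk difference.
3. Code the Week 8 contrast of 2 mg with placebo, and state that its two-sided test on the log-odds scale supplies the primary p-value.
4. State how the promised Week 8 risk difference and its 95% CI come from the same logit model. Standardisation over the covariates and the random effect with a delta-method interval is one way. Report it beside the Week 8 odds ratio, labelled as subject-specific.
5. Minor: either drop the autoregressive sentence and `type=ar(1)`, or code a visit-level structure that matches the text. Either one reconciles them.

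The cost is SAP text and code edits and a short extra estimation step. Data, visits, sample size and covariates do not change.
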